### 6.2.2 Dose Modifications

Table 6.2.2 details the criteria for disrupting treatment, dose modification and treatment discontinuation following an adverse event. See section 6.2.1 for general guidelines including the maximum number of dose reductions. The agent listed in Table 6.2.2 indicates the drug to which the toxicity is likely attributed based on the toxicity profile of the agents. For treatment purposes, the investigator will determine attribution of all toxicities.

**Table 6.2.2 Criteria for Disrupting Treatment, Dose Modification or Discontinuation**

Adverse Event	Agent most likely attributed to toxicity	Treatment modification
Hematological Toxicities		
Thrombocytopenia Grade 1 ( $75 \times 10^9/L$ -<LLN)	Irinotecan, 5-FU	Maintain treatment
Thrombocytopenia Grade 2 ( $50 - <75 \times 10^9/L$ )		Hold all study agents until recovery to $\leq$ grade 1 (plts $\geq 75 \times 10^9/L$ ). Resume treatment with a 20% dose reduction from pre-hold dose of irinotecan and 5-FU; leucovorin and panitumumab resume at pre-hold dose.
Thrombocytopenia Grade 3 ( $25 - <50 \times 10^9/L$ )		Hold all study agents until recovery to $\leq$ grade 1 (plts $\geq 75 \times 10^9/L$ ). Resume treatment with a 20% dose reduction from pre-hold dose of irinotecan and 5-FU; leucovorin and panitumumab resume at pre-hold dose.
Thrombocytopenia Grade 4 ( $<25 \times 10^9/L$ )		Hold all study agents until recovery to $\leq$ grade 1 (plts $\geq 75 \times 10^9/L$ ). Resume treatment with a 40% dose reduction from pre-hold dose of irinotecan and 5-FU; leucovorin and panitumumab resume at pre-hold dose.
Neutropenia (ANC) Grade 1 ( $1.5 \times 10^9/L$ -<LLN)	Irinotecan, 5-FU	Maintain treatment
Neutropenia (ANC) Grade 2 ( $1.0 - <1.5 \times 10^9/L$ )		Maintain treatment

Neutropenia (ANC) Grade 3 ( $0.5 - <1.0 \times 10^9/L$ )		Hold all study agents until recovery to $\leq$ grade 2 (ANC $\geq 1.0 \times 10^9/L$ ). Resume treatment with a 20% dose reduction from pre-hold dose of irinotecan and 5-FU; leucovorin and panitumumab resume at pre-hold dose. The investigator may re-escalate to the original dose in the setting of the addition of prophylactic GCSF support.
Neutropenia (ANC) Grade 4 ( $<0.5 \times 10^9/L$ -<LLN)		Hold all study agents until recovery to $\leq$ grade 2 (ANC $\geq 1.0 \times 10^9/L$ ). Resume treatment with a 20% dose reduction from pre-hold dose of irinotecan and 5-FU; leucovorin and panitumumab resume at pre-hold dose. Consider G-CSF prophylaxis in subsequent cycles.
Anemia $\geq$ Grade 3	Irinotecan, 5-FU	Maintain treatment and manage according to BSC. If per the treating investigator anemia is not adequately managed by transfusion, hold treatment and/or apply a 20% dose reduction of irinotecan and 5-FU and continue leucovorin and panitumumab at pre-hold dose.
Serum Electrolytes		
Serum Electrolytes $\geq$ Grade 2 Calcium , Potassium, Magnesium,	Irinotecan 5-FU (via diarrhea), Panitumumab	Provide supportive care per Section 5.6.6. Maintain treatment per investigator discretion.  No dose reduction for panitumumab or FOLFIRI will be made for electrolyte disturbances. Electrolyte disturbances are managed by aggressive electrolyte replacement.  Study treatment will be withheld for grade 3 and above hypomagnesemia and/or grade 3 and above hypocalcemia and/or hypokalemia that persists despite aggressive replacement therapy.
Gastrointestinal		
Diarrhea Grade 1 (2-3 stools/day >pretreatment)	Irinotecan, 5-FU, Panitumumab	See Section 5.6.5 for management recommendations. Maintain treatment.
Diarrhea Grade 2 (4-6 stools/day > pretreatment)		See Section 5.6.5 for management recommendations. Maintain treatment Recurrent grade 2 toxicities may be addressed by 20% dose reductions of irinotecan and 5-FU and/or a single dose level reduction of panitumumab if deemed appropriate by the treating investigator.
Diarrhea Grade 3 (7-9 stools/day > pretreatment)		See Section 5.6.5 for management recommendations. Hold study treatment until the diarrhea decreases to $\leq$ grade 1, and then restart treatment according to the following:  First event: resume treatment with a 20% dose reduction from pre-hold dose of irinotecan and 5-FU; leucovorin and panitumumab resume at pre-hold dose.  Additional events: resume treatment with a 20% dose reduction from pre-hold dose of irinotecan and 5-FU, and, at the discretion of the investigator, a dose level reduction of panitumumab from the pre-hold dose; leucovorin resumes at pre-hold dose.

Diarrhea Grade 4 (≥10 stools/day > pretreatment)
		
See Section 5.6.5 for management recommendations. Hold study treatment until the diarrhea decreases to ≤ grade 1, and then restart treatment according to the following:
 
First event: resume treatment with a 30% dose reduction from pre-hold dose of irinotecan and 5-FU; leucovorin and panitumumab resume at pre-hold dose.
 
Additional events: resume treatment with a 30% dose reduction from pre-hold dose of irinotecan and 5-FU, and, at the discretion of the investigator, a dose level reduction of panitumumab from the pre-hold dose; leucovorin resumes at pre-hold dose.

Mucositis/Stomatitis Grade 1
		
Maintain treatment


Mucositis/Stomatitis Grade 2
		
Maintain treatment Recurrent grade 2 toxicities may be addressed by 20% dose reductions of irinotecan and 5-FU and/or a single dose level reduction of panitumumab if deemed appropriate by the treating investigator.

Mucositis/Stomatitis Grade 3
		
Hold study treatment until resolution to ≤ grade 1, and then restart treatment according to the following:
 
First event: resume treatment with a 20% dose reduction from pre-hold dose of irinotecan and 5-FU; leucovorin and panitumumab resume at pre-hold dose.
 
Additional events: resume treatment with a 20% dose reduction from pre-hold dose of irinotecan and 5-FU, and, at the discretion of the investigator, a dose level reduction of panitumumab from the pre-hold dose; leucovorin resumes at pre-hold dose.

Mucositis/Stomatitis Grade 4
		
Hold study treatment until resolution to ≤ grade 1, and then restart treatment according to the following:
 
First event: resume treatment with a 30% dose reduction from pre-hold dose of irinotecan and 5-FU; leucovorin and panitumumab resume at pre-hold dose.
 
Additional events: resume treatment with a 30% dose reduction from pre-hold dose of irinotecan and 5-FU, and, at the discretion of the investigator, a dose level reduction of panitumumab from the pre-hold dose; leucovorin resumes at pre-hold dose.

Vomiting or Nausea Grade 1
	
Irinotecan, 5-FU, Panitumumab
	
Maintain treatment

Vomiting or Nausea Grade 2
		
Hold all study treatments until resolution to ≤ grade 1 and then resume treatment at pre-hold dose.

Vomiting or Nausea Grade 3 or Grade 4, despite appropriate medical management		
Hold study treatment until resolution to <math>\leq</math> grade 1, and then restart treatment according to the following:
 
First event: resume treatment with a 20% dose reduction from pre-hold dose of irinotecan and 5-FU; leucovorin and panitumumab resume at pre-hold dose.
 
Additional events: resume treatment with a 20% dose reduction from pre-hold dose of irinotecan and 5-FU; leucovorin resumes at pre-hold dose.

Infusion reaction		
Infusion reaction- grade 1 or 2		
Provide supportive care per institutional standard practice.
 
For infusion reaction to panitumumab, reduce the infusion rate by 50% for the duration of that infusion.
 
For infusion reaction to irinotecan decrease the infusion rate as deemed appropriate by the investigator.
 
Depending on the severity and/or persistence of the reaction, the treating investigator may consider decreasing the infusion rate and administering pre-medications for future administrations.

Infusion reaction Grade 3 or Grade 4		
Immediately stop the infusion. Depending on the severity and/or persistence of the reaction the treating investigator may consider permanently discontinuing study treatment and/or reducing the rate of infusion with appropriate premedications.

Respiratory		
Confirmed interstitial lung disease.	Irinotecan, panitumumab	Permanently discontinue all study treatments.
Skin and Subcutaneous Tissue Toxicities		
NOTE: Use Appendix B for grading of skin and subcutaneous tissue toxicities.		
Hand and Foot Grade 1	5-FU	Maintain treatment
Hand and Foot Grade 2 or Grade 3 considered at least possibly related to 5-FU		Hold study treatment until resolution to $\leq$ grade 1 or baseline, and then restart treatment with a 20% reduction of 5-FU from pre-hold dose; all other agents will resume at pre-hold dose.
Hand and Foot Grade 4 considered at least possibly related to 5-FU		Hold all treatment until resolution to $\leq$ grade 1 or baseline, then resume treatment with a 30% reduction of 5-FU from pre-hold dose; all other agents will resume at pre-hold dose.
Any skin or nail Grade 2 toxicity considered at least possibly related to panitumumab that meets any of the following criteria: Requires IV antibiotic or IV antifungal treatment, needs surgical debridement, meets the definition of "serious" (defined in Section 7.3)	Panitumumab	
Hold all treatments until improvement: IV antibiotic or IV antifungal treatment is no longer required, recovered from surgical debridement, skin or nail related toxicity is no longer serious.
 
First occurrence: resume study agents at pre-hold dose.
 
Additional occurrences: resume panitumumab with a single dose level reduction from pre hold dose, and resume all other agents at pre-hold dose.

Any skin or nail Grade 3 toxicity considered at least possibly related to panitumumab		Hold all treatments until improvement: AE has improved to $\leq$ grade 2 or baseline, IV antibiotic or IV antifungal treatment is no longer required, recovered from surgical debridement, skin or nail related toxicity is no longer serious.  First occurrence: resume study agents at pre-hold dose.  Additional occurrences: resume panitumumab with a single dose level reduction from pre hold dose, and resume all other agents at pre-hold dose.
Any skin or nail Grade 4 toxicity considered at least possibly related to panitumumab		Permanently discontinue study agents.
Other unspecified Non-Hematologic Toxicities considered clinically significant and Related to FOLFIRI		
Grade 1	5-FU, irinotecan	Maintain treatment
Grade 2		Hold treatment until resolution to $\leq$ grade 1 or baseline, then resume treatment at pre-hold dose.
Grade 3		Hold treatment until resolution to $\leq$ grade 1 or baseline, then resume treatment with a 20% dose reduction from pre-hold dose of irinotecan and 5-FU and resume other study agents at pre-hold doses.
Grade 4		Hold treatment until resolution to $\leq$ grade 1 or baseline, then resume treatment with a 30% dose reduction from pre-hold dose of irinotecan and 5-FU and resume other study agents at pre-hold doses.
Other unspecified Non-Hematologic Toxicities considered Related to Panitumumab		
Grade 1	Panitumumab	Maintain treatment
Grade 2		Maintain treatment
Grade 3		Hold treatment until resolution to $\leq$ grade 1 or baseline, then resume according to the following.  First occurrence: resume study agents at pre hold dose.  Additional occurrences: resume panitumumab with a single dose level reduction from pre hold dose, and resume all other agents at pre-hold dose.
Grade 4		Permanently discontinue study treatment.
Other unspecified Non-Hem Toxicities considered UNRELATED to study agents		
Other unspecified events of any grade considered unlikely to be related or not related to study agents.	UNRELATED	Maintain treatment with study agents. Interruption of study treatment is permitted if the investigator consults with the Principal Investigator to determine that this is in the best interest of the participant.

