### 5.6.7 Management of Panitumumab-associated Infusion Reaction

Infusion-related reactions include cytokine release syndromes/acute infusion reaction and allergic/hypersensitivity reactions as defined by the CTCAE version 4.0. Participants who experience any grade of infusion reaction during panitumumab administration will have the infusion stopped. Continuation of dosing will be based on the severity and resolution of the event. For grade 1 or 2 reactions, reduce the infusion rate by 50%. The infusion should be immediately stopped for grade 3 or 4 reactions. Depending on the severity and/or persistence of the reaction consider permanently discontinuing panitumumab.

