## 6.2 Dose Modifications/Delays

### 6.2.1 General Information

1. The study will use the NCI Common Terminology Criteria for Adverse Events (CTCAE) version 4.0 to grade toxicities, except for skin- and nail-related toxicities, which must be graded using CTCAE version 4.0 with modifications found in Appendix B. A copy of the version 4.0 can be downloaded from:

<http://evs.nci.nih.gov/ftp1/CTCAE/About.html>

2. Study agents are always held together, regardless of the attribution of the toxicity.
3. There is no maximum dose reduction for irinotecan or 5-FU.
4. Panitumumab has a maximum of two dose level reductions, and will not exceed the 60% dose level according the following table:

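### Table 6.2.2 says both to resume and to stop permanently when one Grade 4 event is attributed to panitumumab and to 5-FU or FOLFIRI, and no rule says which row governs

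*Combined protocol and SAP*

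**What the plan says.** Table 6.2.2 lists toxicities by type, grade and likely responsible agent. Section 6.2.2 leaves attribution to the investigator.

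Two skin rows matter most. The first is triggered by "Hand and Foot Grade 4 considered at least possibly related to 5-FU". All treatment is held until recovery, and the row ends "then resume treatment with a 30% reduction of 5-FU from pre-hold dose; all other agents will resume at pre-hold dose". The second is triggered by "Any skin or nail Grade 4 toxicity considered at least possibly related to panitumumab", and its instruction is "Permanently discontinue study agents".

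For toxicities without a row of their own, the table has one block for events related to FOLFIRI and another headed "Other unspecified Non-Hematologic Toxicities considered Related to Panitumumab". At Grade 4 the FOLFIRI block holds and then resumes with irinotecan and 5-FU reduced. The panitumumab block discontinues permanently.

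Section 6.2.1, item 2, adds that "Study agents are always held together, regardless of the attribution of the toxicity". The note above the skin rows sends grading to Appendix B.

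Infusion reactions appear twice. Section 5.6.7 says "Participants who experience any grade of infusion reaction during panitumumab administration will have the infusion stopped" and then goes on to a 50% rate reduction for Grade 1 or 2. The table says "For infusion reaction to panitumumab, reduce the infusion rate by 50% for the duration of that infusion".

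**The concern.** A management table organised by responsible drug works only if an event reaches one row, or if the text says what to do when it reaches two. All four drugs are given together every cycle, so joint attribution is foreseeable, particularly where the threshold is only possible relatedness. If the two rows then give opposite answers on whether the participant continues, the protocol cannot be followed as written.

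What is at stake is first participant safety, because these are Grade 4 events. Second is consistency: two participants with the same event could be managed in opposite ways, each in line with one row and contrary to the other. That also clouds deviation reporting, since Section 12.3.2 requires every deviation to be reported within five days. Third, exposure to treatment, and through it response and PFS, could depend on the row chosen.

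**Working it through.** No figure in the plan is in dispute, so the check is a comparison of texts.

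**1. The two Grade 4 pairs**

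| Pair | Row | Trigger | Instruction |
|---|---|---|---|
| a | Hand-foot Grade 4 | At least possibly related to 5-FU | Hold, then resume: 5-FU reduced by 30%, other agents at pre-hold dose |
| a | Any skin or nail Grade 4 | At least possibly related to panitumumab | Permanent discontinuation |
| b | Other unspecified Grade 4, FOLFIRI | Related to FOLFIRI and clinically significant | Hold, then resume: irinotecan and 5-FU reduced by 30%, others at pre-hold dose |
| b | Other unspecified Grade 4, panitumumab | Related to panitumumab | Permanent discontinuation |

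In pair a, the second row covers any skin toxicity and does not carve out hand-foot events. Both triggers use the same low threshold, so one event can satisfy both. In pair b, the wording is simply related, which is narrower, but nothing prevents an event being related to both. Fatigue is listed for panitumumab (Section 6.1.1) and for irinotecan (Section 6.1.2) and has no row of its own. In either pair, resuming and discontinuing permanently cannot both be done.

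**2. Grade 3 skin rows**

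The hand-foot row requires recovery to Grade 1 or baseline and resumes with 5-FU reduced by 20%. The panitumumab row requires recovery to Grade 2 or baseline and resumes 5-FU at the pre-hold dose. Recovery to Grade 1 also meets the Grade 2 threshold, so the main conflict is the 5-FU dose. Both rows resume treatment.

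**3. Does any other text settle the order?**

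- Section 6.2.2, investigator attribution: settles it if one agent is named, and is silent if two are.
- Section 6.2.1, item 2: governs holding, not what follows a hold.
- Section 6.2.1, item 7: permits, with the Principal Investigator's approval, holds or reductions that the table does not outline. Here the table outlines both actions.
- Section 6.2.1, item 8: concerns events judged unlikely to be related to treatment.
- Section 12.3.3: has the pharmacy turn to the Principal Investigator when the protocol is ambiguous. That is a case-by-case route, not a precedence rule.

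**4. Grading**

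Appendix B has rows for nail changes, erythema, pruritus, acneiform rash, rash/desquamation and ulceration. It has none for hand-foot. A hand-foot event might therefore be graded under Appendix B's erythema row, which reaches Grade 4, or under unmodified CTCAE version 4.0. The choice bears on which Table 6.2.2 row is read.

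**5. Weight of one participant**

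1/25 = 4% of the full sample and 1/14 = 7.1% of the first stage. This is the weight of a single case, not an estimate of how many will be affected.

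**The case against.** The best defence is that the overlap is narrow. The table names 5-FU alone for hand-foot events, and Section 6.1 lists palmar-plantar erythrodysesthesia for 5-FU and not for panitumumab. The investigator will often name a single agent. The trial runs at one site, where the Principal Investigator can resolve doubtful cases. All of this stands and makes the conflict less frequent. It does not tell the site what to do once two agents are named.

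Several stronger readings are tempting, and the documents do not support them.

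- *The infusion-reaction passages disagree on who stays on treatment.* Section 5.6.7 itself goes on to halve the rate for Grade 1 or 2, so stopping and then continuing at half rate is compatible with the table, which merely omits the stop. For Grade 3 or 4, Section 5.6.7 speaks of discontinuing panitumumab and the table of discontinuing study treatment, but both only ask the investigator to consider it. The table's infusion-reaction rows also cover irinotecan. This is an alignment matter.
- *The unspecified Grade 2 rows, hold versus maintain, cannot both be followed.* The joint-hold rule largely answers this: if one row requires a hold, all agents are held.
- *Grade 4 toxicities in general get contradictory instructions.* The Grade 4 platelet, neutrophil, diarrhea, mucositis and vomiting rows have no competing row.
- *Dehydration and renal failure are further dual-listed examples.* They are weak ones. The renal entries for both drugs, and dehydration for irinotecan, are described as consequences of gastrointestinal effects or dehydration, and diarrhea has its own rows.

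**Conclusion.** The contradiction is in the text and should be corrected. It is confined to two Grade 4 row pairs, with a lesser difference in 5-FU dose between the Grade 3 skin rows. It arises only when an event is attributed to both panitumumab and 5-FU or FOLFIRI.

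The statistical consequence is indirect. A reader might infer that PFS or discontinuation for toxicity becomes uninterpretable, but that goes too far. PFS counts progression or death, so stopping for toxicity is not an event, and Table 10.0 plans progression follow-up after treatment. That follow-up is weaker than on-treatment imaging, because footnote z says omitting it is not a deviation. The row chosen could therefore affect exposure, the chance of response and how progression is ascertained. At the interim look, one participant could change the decision only if the counts sat on the boundary: no response versus one, or three versus four progression-free at 4 months. The documents give neither a Grade 4 rate nor a frequency of joint attribution, so no effect size can be stated.

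**What to change.** Reconcile the conflicting rows. Either state in Section 6.2.1 which row governs when an event is attributed to more than one agent, or reword the triggers so that they are mutually exclusive. The same rule should cover the Grade 3 skin rows. State the grading source for hand-foot events, given that Appendix B has no such row.

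As a minor alignment, make Section 5.6.7 and the infusion-reaction rows agree on whether a Grade 1 or 2 reaction involves an initial stop, and on which agents a Grade 3 or 4 discontinuation covers.

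Which instruction should prevail is a clinical decision for the sponsor, and no view is taken here. The cost is a protocol wording amendment, with no added participants, procedures or staff.

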## **7.0 DATA AND SAFETY MONITORING, UNANTICIPATED PROBLEMS AND ADVERSE EVENT REPORTING**

### **7.1 Definition of Risk Level**

This is a Risk Level 3 study, as defined in the “City of Hope Data and Safety Monitoring Plan”, <http://www.coh.org/dsmc/Pages/forms-and-procedures.aspx> because it is a Phase II clinical trial where

the risks are at least balanced by the potential benefit to participants and the importance of the knowledge that may result.

## 7.2 Monitoring and Personnel Responsible for Monitoring

The Protocol Management Team (PMT) consisting of the PI, Collaborating Investigator, CRA, protocol nurse, and statistician is responsible for monitoring the data and safety of this study, including implementation of any stopping rules for safety and efficacy.

**Table 7.2.1 City of Hope PMT Reporting Timelines for the DSMC**

Risk Level	Phase	Standard Reporting Requirement
RL 1, RL2, and Expanded Access Studies		No reports required
3	I	Every 3 months from activation date, as indicated in MIDAS
3	Pilot, Feasibility, II-IV	Every 6 months from activation date, as indicated in MIDAS
4	Pilot, Feasibility, I-IV	Every 3 months from activation date, as indicated in MIDAS

Data and safety will be reported to the COH DSMC using the PMT report and submitted according to the timelines in Table 1 above. Protocol specific data collection will include the following items: toxicity information, RR, PFS, OS.

## 7.3 Definitions

**Adverse event (AE)** - An adverse event is any untoward medical experience or change of an existing condition that occurs during or after treatment, whether or not it is considered to be related to the protocol intervention.

**Unexpected Adverse Event [21 CFR 312.32 (a)]** – An adverse event is unexpected if it is not listed in the investigator’s brochure and/or package insert; is not listed at the specificity or severity that has been observed; is not consistent with the risk information described in the protocol and/or consent; is not an expected natural progression of any underlying disease, disorder, condition, or predisposed risk factor of the research participant experiencing the adverse event.

**Expected Adverse Event** - Any event that does not meet the criteria for an unexpected event OR is an expected natural progression of any underlying disease, disorder, condition, or predisposed risk factor of the research participant experiencing the adverse event.

**Serious Adverse Event (SAE) [21 CFR 312.32]** - defined as any expected or unexpected adverse event that results in any of the following outcomes:

- Death
- Is life-threatening experience (places the participant at immediate risk of death from the event as it occurred)
- Unplanned hospitalization (equal to or greater than 24 hours) or prolongation of existing hospitalization
- A persistent or significant disability/incapacity

- A congenital anomaly/birth defect
- Secondary malignancy
- Any other adverse event that, based upon appropriate medical judgment, may jeopardize the participant’s health and may require medical or surgical intervention to prevent one of the outcomes listed above (examples of such events include allergic bronchospasm requiring intensive treatment in the emergency room or at home, blood dyscrasias or convulsions that do not result in inpatient hospitalization, or the development of drug dependency or drug abuse).

**Unanticipated problem (UP)** – Any incident, experience, or outcome that **meets all three** of the following criteria:

1. Unexpected (in term nature, severity, or frequency) given the following: a) the research procedures described in the protocol-related documents such as the IRB approved research protocol, informed consent document or Investigator Brochure (IB); and b) the characteristics of the participant population being studied; **AND**
2. Related or possibly related to participation in the research (possibly related means there is a reasonable possibility that the incident, experience, or outcomes may have been caused by the drugs, devices or procedures involved in the research); **AND**
3. Suggests that the research places participants or others at greater risk of harm (including physical, psychological, economic, or social harm) than previously known or recognized.

